4.2.3.1.2 Viral Resistance Measurements

HCV resistance measurements

Resistance-associated variants (RAVs) of the hepatitis C virus can lead to increased risk of failure to DAA therapy. In addition, subjects with virologic failure may develop RAVs.

Blood samples for viral resistance assays are collected on all subjects at Baseline (Day 1) to determine the impact of baseline RAVs on response to EBR and GZR.

To better understand the presence of RAVs after treatment with a regimen containing EBR/GZR, samples will be collected at virologic failure confirmation visits and all follow-up visits after virologic failure is confirmed. Samples will be tested for any subject meeting virologic failure criterion who has detectable virus >1000 IU/mL. These same subjects who meet any virologic failure criterion will have samples collected at all subsequent follow-up visits to be assessed for RAVs, if the virus is detectable and >1000 IU/mL.

Subjects who fail due to early discontinuation of study medication and continue in the trial will also have samples collected and tested for RAVs at each follow-up visit, if the virus is detectable and >1000 IU/mL.

Analysis of RAVs will entail a variety of techniques that may include population sequencing and/or next generation sequencing. Additionally, genotypic and investigational assays may be employed to differentiate virologic failure from re-infection. Resistance testing may also be performed on leftover HCV RNA plasma samples.

4.2.3.2 Safety Endpoints

The safety and tolerability of the study regimens will be assessed by a clinical evaluation of AEs and inspection of other study parameters including vital signs, physical examinations, and standard laboratory safety tests at appropriate time points as specified in the Trial Flow Chart (Section 6.0). Adverse events are graded and recorded according to Section 7.2. Subjects may be asked to return for unscheduled visits in order to perform additional safety monitoring.

4.2.3.3 Planned Exploratory Biomarker Research

Planned Genetic Analysis

Understanding genetic determinants of drug response is an important endeavor during medical research. This research will evaluate whether genetic variation within a clinical trial population correlates with response to the treatment(s) under evaluation. If genetic variation is found to predict efficacy or adverse events, the data might inform optimal use of therapies in the patient population. This research contributes to understanding genetic determinants of efficacy and safety associated with the treatments in this study.

In addition to studying variation across the human genome, for example, *IL28B* genetic variants will specifically be investigated for understanding variation in clinical endpoints for example, but not limited to, SVR and other efficacy and safety measurements.

4.2.3.4 Future Biomedical Research

The Sponsor will conduct Future Biomedical Research on specimens collected for future biomedical research during this clinical trial. This research may include genetic analyses (DNA), gene expression profiling (RNA), proteomics, metabolomics (serum, plasma) and/or the measurement of other analytes.

Such research is for biomarker testing to address emergent questions not described elsewhere in the protocol (as part of the main trial) and will only be conducted on specimens from appropriately consented subjects. The objective of collecting specimens for Future Biomedical Research is to explore and identify biomarkers that inform the scientific understanding of diseases and/or their therapeutic treatments. The overarching goal is to use such information to develop safer, more effective drugs/vaccines, and/or to ensure that subjects receive the correct dose of the correct drug/vaccine at the correct time. The details of this Future Biomedical Research sub-trial are presented in Section 12.2 - Collection and Management of Specimens for Future Biomedical Research. Additional informational material for institutional review boards/ethics committees (IRBs/ERCs) and investigational site staff is provided in Section 12.3.

4.3 Benefit/Risk

It cannot be guaranteed that subjects in clinical trials will directly benefit from treatment during participation, as clinical trials are designed to provide information about the safety and effectiveness of an investigational medicine.

Elbasvir/Grazoprevir

In Phase 1-3 studies, 1234 healthy volunteers, 66 non-HCV-infected persons with liver or kidney impairment, and 2704 HCV-infected subjects have been treated with any dose or regimen of EBR and/or GZR, with or without RBV. At a dose of EBR (50 mg) and GZR (100mg) in ~ 2000 subjects, high efficacy and a favorable safety profile has been demonstrated including subjects with cirrhosis, HIV co-infection, chronic kidney disease and history of prior HCV treatment failure.

Additional details regarding specific benefits and risks for subjects participating in this clinical trial may be found in the accompanying IB and Informed Consent documents.

5.0 METHODOLOGY

5.1 Entry Criteria

5.1.1 Diagnosis/Condition for Entry into the Trial

Male/Female subjects with chronic HCV GT4 infection who are at least 18 years of age will be enrolled in this trial.

5.1.2 Subject Inclusion Criteria

In order to be eligible for participation in this trial, the subject must:

1. be \geq 18 years of age on day of signing informed consent
2. be a current resident of France
3. have HCV RNA (\geq 10,000 IU/mL in peripheral blood) at the time of screening
4. have documented chronic HCV GT4 (with no evidence of non-typeable or mixed genotype) infection and meet the definition below:
 - a. positive for anti-HCV antibody, HCV RNA, or HCV GT4 at least 6 months before screening, **or**
 - b. positive for anti-HCV antibody or HCV RNA at screening with a liver biopsy consistent with chronic HCV infection (or a liver biopsy performed before enrollment with evidence of CHC disease, such as the presence of fibrosis)
5. have one of the below liver staging assessments as follows:
 - a. Liver biopsy performed within 24 months of Day 1 of this study (if subject has cirrhosis, there is no time restriction on biopsy)

b. FibroScan® performed within 12 months of Day 1 of this study with interpretable result in kilopascals (kPa) as follows

- Fibrosis score of F0-F2 = <8.0 kPa
- Fibrosis score of F3 = 8.0 – 12.5 kPa
- Cirrhosis (F4) = >12.5 kPa

c. For cirrhotic (F4) subjects only: A FibroTest® (FibroSure®)* performed during Screening with a score of >0.75 **and** an aspartate aminotransferase (AST): platelet ratio index (APRI) of >2.

APRI formula: AST ÷ lab upper limit of normal (ULN) for AST x 100 ÷ (platelet count ÷ 100) (APRI calculation to be provided by the central laboratory).

*If FibroTest®/APRI results are not available or if the FibroTest®/APRI score is indeterminant then either a liver biopsy or interpretable FibroScan® result, performed within timeframe above, must be obtained and reported for study entry and liver fibrosis staging.

NOTE: In cases where more than one liver fibrosis staging assessment is available, only one result may be used to determine fibrosis status.

6. have a prior treatment history of either of the following (see Section 7.1.5 for definitions):

- a. HCV treatment-naïve (TN)
- b. HCV treatment-experienced (TE) with IFN +/- RBV +/- SOF:
 - On-treatment Failure
 - Relapser
 - Other/intolerant

NOTE: When available, documentation of prior IFN +/- RBV +/- SOF treatment history should include clinic notes or referral letter documenting regimen administered, approximate dates of treatment, approximate date of virologic failure, and a history of laboratory confirmed prior virologic failure or documented intolerance to allow for categorization of prior regimen. If the subject was treated with a regimen more than once, the categorization must be based on the most recent round of treatment.

7. meet one of the following categories:

- a. the subject is a male.
- b. the subject is a female who is not of reproductive potential, defined as a female who either: (1) is postmenopausal (defined as at least 12 months with no menses in women \geq 45 years of age); (2) has had a hysterectomy and/or bilateral oophorectomy, bilateral salpingectomy, or bilateral tubal ligation/occlusion at least 6 weeks prior to screening; OR (3) has a congenital or acquired condition that prevents childbearing.

c. the subject is a female who is of reproductive potential and agrees to avoid becoming pregnant from Day 1 through 14 days after the last dose of study drug or longer if dictated by local regulations by complying with one of the following: (1) practice abstinence[†] from heterosexual activity OR (2) use (or have her partner use) acceptable contraception during heterosexual activity. Acceptable methods of contraception are[‡]:

Single method (one of the following is acceptable):

- intrauterine device (IUD)
- vasectomy of a female subject's male partner
- contraceptive rod implanted into the skin

Combination method (requires use of 2 of the following):

- diaphragm with spermicide (cannot be used in conjunction with cervical cap/spermicide)
- cervical cap with spermicide (nulliparous women only)
- contraceptive sponge (nulliparous women only)
- male condom or female condom (cannot be used together)
- hormonal contraceptive: oral contraceptive pill (estrogen/progestin pill or progestin-only pill), contraceptive skin patch, vaginal contraceptive ring, or subcutaneous contraceptive injection

[†]Abstinence (relative to heterosexual activity) can be used as the sole method of contraception if it is consistently employed as the subject's preferred and usual lifestyle and if considered acceptable by local regulatory agencies and ERCs/IRBs. Periodic abstinence (e.g., calendar, ovulation, sympto-thermal, post-ovulation methods, etc.) and withdrawal are not acceptable methods of contraception.

[‡]If a contraceptive method listed above is restricted by local regulations/guidelines, then it does not qualify as an acceptable method of contraception for subjects participating at sites in this country/region.

8. understands the study procedures, alternative treatments available, risks involved with the study, and voluntarily agrees to participate by giving written informed consent.
9. provides written informed consent for the trial. The subject may also provide consent for future biomedical research (FBR). However, the subject may participate in the main trial without participating in FBR.

For HIV co-infected subjects, these additional criteria must also be met:

10. have HIV-1 infection documented at any time prior to screening by any licensed rapid HIV test or HIV enzyme or chemiluminescence immunoassay (E/CIA) test kit and confirmed by a licensed Western blot or a second antibody test by a method other than the initial rapid HIV and/or E/CIA, or by HIV-1 p24 antigen, or plasma HIV-1 RNA viral load.

11. meet one of the following criteria:

- a. If not currently on antiretroviral therapy (ART) and has no plan to initiate ART treatment while participating in this study:
 - i. Subjects not on ART must have CD4+ T-cell count > 500 cells/mm³ at screening.
- b. have well controlled HIV on ART, defined as:
 - i. must have achieved and maintained virologic suppression (defined as confirmed HIV RNA level below the LLOQ of available assay) on HIV ART at least 8 weeks prior to study entry (Day 1).
 - a) ART regimen must contain only the following antiretroviral medications: tenofovir, abacavir, lamivudine, emtricitabine, raltegravir, dolutegravir, and rilpivirine.
 - b) Dose modifications or changes in drugs during the 4 weeks prior to study entry (Day 1) are not permitted.
 - ii. have HIV RNA $<$ LLOQ at screening
 - iii. subjects on ART must have a CD4+ T-cell count > 200 cells/mm³ at screening.

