11. is a female and is pregnant or breastfeeding, or expecting to conceive or donate eggs from Day 1 through 14 days after the last dose of study drug or longer if dictated by local regulations, OR a male subject who is expecting to donate sperm from Day 1 through 14 days after the last dose of study drug or longer if dictated by local regulations.
12. has any clinically-significant illness (other than HCV) or any other major medical disorder that in the opinion of the investigator may interfere with subject treatment, assessment or compliance with the protocol or any medical/surgical conditions that may result in a need for hospitalization during the period of the study; subjects currently under evaluation for a potentially clinically-significant illness (other than HCV) are also excluded.

NOTE: Subjects with a history of acute non-HCV-related hepatitis, which resolved > 6 months before study entry, can be enrolled.

13. has exclusionary laboratory values at the screening visit as listed in [Table 10](#)

NOTE: If any of the laboratory exclusion criteria in [Table 10](#) are met, the site may have the abnormal value retested once. No other tests may be repeated for determining study entry eligibility.

Table 10 Laboratory Exclusion Criteria

Laboratory Assessment	Exclusionary Parameters
Hemoglobin	< 10 g/dL in females or < 11 g/dL in males
Platelets	< $40 \times 10^3/\mu\text{L}$
Serum Albumin	< 3.0 g/dL
INR	> 1.7 (unless subject has known hemophilia or is stable on an anticoagulant regimen affecting INR)
ALT	> $10 \times \text{ULN}$
AST	> $10 \times \text{ULN}$

14. Is or has an immediate family member (e.g., spouse, parent/legal guardian, sibling or child) who is investigational site or sponsor staff directly involved with this trial.

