5.3 Randomization or Treatment Allocation

In this open-label, partially randomized study, approximately 120 subjects will be enrolled. Approximately 75 (minimum of 60) TN subjects with stage 0-2 fibrosis will be randomized 2:1 to Arms 1 and 2, respectively. A total of approximately 45 TN subjects with stage 3-4 fibrosis and TE subjects with stage 0-4 fibrosis will be assigned (not randomized) to Arm 2. The treatment allocation ([Table 1](#)) will be implemented centrally using an interactive voice response system/integrated web response system (IVRS/IWRS).

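### The APRI formula in inclusion criterion 5c has no platelet unit and, as printed, does not fit its own cut-off of >2; Section 7.1.2.6 conflicts with 5c and with itself

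*Combined protocol and SAP*

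**What the plan says.** Under criterion 5 of Section 5.1.2 a subject must "have one of the below liver staging assessments as follows": biopsy (5a), FibroScan (5b), or FibroTest with APRI (5c). Route 5c is "For cirrhotic (F4) subjects only" and requires both FibroTest >0.75 and APRI >2. The formula is printed as "APRI formula: AST ÷ lab upper limit of normal (ULN) for AST x 100 ÷ (platelet count ÷ 100", followed by a closing bracket, with no unit for the platelet count. A note adds "APRI calculation to be provided by the central laboratory". If the FibroTest/APRI result is missing or indeterminate, a biopsy or an interpretable FibroScan, "performed within timeframe above, must be obtained and reported for study entry and liver fibrosis staging". Where several assessments exist, "only one result may be used to determine fibrosis status"; which one is not stated.

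"Table 10 Laboratory Exclusion Criteria" in Section 5.1.3 excludes platelets below 40 × 10³/µL and AST above 10 × ULN.

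Section 7.1.2.6 says the study applies a published FibroTest/APRI algorithm with one variation: both tests must point to no cirrhosis. One sentence gives the cut-offs ≤1 and ≤0.48 for FibroTest and APRI, in that order. The next gives APRI ≤1 and FibroTest ≤0.48. The 5c cut-offs of >0.75 and >2 do not appear there.

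Under Section 5.3, treatment-naïve (TN) F0-F2 subjects are randomised 2:1, while TN F3-F4 and all treatment-experienced (TE) subjects "will be assigned (not randomized) to Arm 2". Section 8.10 defines subgroups by cirrhosis status and by fibrosis stage.

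**The concern.** A cut-off is useful only if the index can fall on either side of it among subjects who could be enrolled. The printed formula contains two factors of 100 that multiply to 10,000, and the missing unit leaves a further factor of 1000 open. If APRI >2 is met by practically everyone, the requirement for both tests in 5c collapses to FibroTest alone. If it is met by practically no one, the route is unusable.

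The first case matters for the trial. A TN subject who is truly F0-F2 but has FibroTest >0.75 could be labelled F4 and sent to Arm 2 instead of being randomised. That subject would be lost from the TN F0-F2 analysis and would sit in the wrong cirrhosis and fibrosis subgroups. The TN F3-F4 cell has a target of 25 and a minimum of 15, so one such subject would be 1/25 = 4% to 1/15 = 6.7% of it.

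Section 7.1.2.6 does not help a reader recover the intended rule, because it describes a different purpose and contradicts itself on which cut-off belongs to which test.

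**Working it through.** **Inputs.** Formula and cut-off >2: criterion 5c. Platelets at least 40 × 10³/µL and AST at most 10 × ULN: Table 10. Platelet values of 150, 250 and 400 × 10³/µL are illustrative assumptions. The plan gives no worked APRI value to reproduce.

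**Step 1: simplify.** (AST/ULN) × 100 ÷ (platelets/100) = 10,000 × (AST/ULN) ÷ platelets. Setting this equal to 2 gives AST/ULN = platelets/5000, in whichever unit platelets are entered.

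**Step 2: evaluate under the two plausible units.**

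| Platelets (10³/µL) | APRI at AST = ULN, 10³/µL | APRI at AST = ULN, cells/µL | AST/ULN needed for >2, 10³/µL | AST/ULN needed for >2, cells/µL |
|---|---|---|---|---|
| 40 | 250 | 0.25 | 0.008 | 8 |
| 150 | 66.7 | 0.067 | 0.03 | 30 |
| 250 | 40 | 0.04 | 0.05 | 50 |
| 400 | 25 | 0.025 | 0.08 | 80 |

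- *10³/µL.* A subject fails >2 only if platelets are at least 5000 × (AST/ULN): 5,000 × 10³/µL at AST = ULN, 2,500 at 0.5 × ULN, 1,250 at 0.25 × ULN. APRI therefore excludes essentially nobody.
- *cells/µL.* At the AST limit of 10 × ULN, APRI = 100,000 ÷ platelets: 2.5 at 40,000, 2.22 at 45,000, 2.0 at 50,000 and 0.4 at 250,000. Exceeding 2 needs platelets from 40,000 to below 50,000 and AST above 8 × ULN (40,000/5000 = 8).

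**Step 3: other readings.** With AST from 0.5 to 10 × ULN and platelets from 40 to 400 × 10³/µL:

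- Platelets in cells/L give at most 2.5 × 10⁻⁶, so never >2.
- Platelets in 10⁴/µL give 125 to 25,000, so always >2.
- Reading the expression as AST ÷ (ULN × 100) ÷ (platelets/100) gives at most 0.25 in 10³/µL and 0.00025 in cells/µL. In 10⁴/µL it gives 0.0125 to 2.5, again nearly unreachable.

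No unit or grouping tried makes >2 a working cut-off.

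**Step 4: would one factor of 100 fit?** Keeping only one factor of 100, with platelets in 10³/µL, >2 needs AST above 0.8, 3, 5 and 8 × ULN at platelets of 40, 150, 250 and 400. The cut-off then separates enrollable subjects. This shows only that the cut-off and that scale are compatible. The documents give no second formula, so what was intended cannot be read from them.

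**Step 5: a character lost in PDF reading.** Assume the divisor was 1000. At AST = ULN and platelets of 250 × 10³/µL:

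- entered as 250: 100 ÷ (250/1000) = 400
- entered as 250,000: 100 ÷ (250,000/1000) = 0.4

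The missing unit still decides the result.

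**Step 6: Section 7.1.2.6 beside 5c.** 5c needs APRI >2. Section 7.1.2.6 needs APRI ≤1 or ≤0.48, depending on which sentence is followed. No subject can satisfy both full rules under either order. These are conflicts of purpose and wording; they do not produce overlapping classifications.

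**The case against.** The strongest reply concerns consequence. The laboratory calculates APRI, and nothing shows that it programmed the printed line. Had it done so in 10³/µL, values of 12.5 to 2,500 over the grid above would have stood out against a cut-off of 2. Harm also needs several further conditions:

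- The site requests FibroTest, which Table 12 makes optional.
- The score exceeds 0.75.
- The 5c result is the one used.
- The subject is TN (TE subjects go to Arm 2 at any stage) and truly F0-F2 (a TN F3 subject called F4 goes to Arm 2 anyway).
- The verification of cirrhosis status in Section 7.1.5.1 does not catch it.

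Staging precedes allocation, so the randomised groups stay comparable. The trial is estimation only. The cells/µL reading misstages nobody; it sends subjects to biopsy or FibroScan. A lost zero in the divisor cannot be excluded. In Section 7.1.2.6, one order can be read as describing the published algorithm and the other as the study's own rule, and eligibility is set by Section 5.1 in any case. The silence on which staging result to use would exist whatever the APRI formula.

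All of this stands as a limit on impact. It does not repair the rule. Table 10's platelet unit is the only one in the protocol, and in that unit the printed formula makes an operative inclusion criterion ineffective. The unit is missing whether or not a character was lost. Because the plan gives no priority among staging results, a discordant FibroScan would not automatically override 5c.

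**Conclusion.** The point holds and should be corrected. As printed, the APRI part of 5c admits almost everyone in 10³/µL and almost no one in cells/µL, and the missing unit alone is a 1000-fold ambiguity. Only the 10³/µL reading could misstage a subject, and only if the central laboratory used the printed formula. That is a risk and has not been demonstrated. The documents do not say how many subjects were staged by 5c, so the number affected cannot be estimated. What is exposed is the allocation of some TN subjects and the Section 8.10 cirrhosis and fibrosis subgroups. Sample size and Tables 17 and 18 do not change. The Section 7.1.2.6 conflicts are wording errors that do not by themselves alter staging. Confidence is moderate, mainly because the laboratory's actual formula is unknown and a lost character is possible.

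**What to change.** Restate the formula in criterion 5c with an explicit platelet unit, on a scale on which the stated cut-off can discriminate, and confirm it against the central laboratory's calculation. If the printed version was applied, recheck every subject staged F4 by 5c. Reconcile Section 7.1.2.6 with 5c on purpose (establishing F4 or showing no cirrhosis) and on which cut-off belongs to which test. The sponsor must settle the cut-offs; none is proposed here. The cost is wording in two sections and one laboratory query, with no new procedures.

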5.1.3 Subject Exclusion Criteria

The subject must be excluded from participating in the trial if the subject:

1. is under the age of legal consent, is mentally or legally incapacitated, has significant emotional problems at the time of pre-study screening visit or expected during the conduct of the study or has a history of a clinically significant psychiatric disorder which, in the opinion of the investigator, would interfere with the study procedures.
2. had prior treatment (defined as 1 dose or more) with DAA therapy not listed in **Section 7.1.5.1**.
3. has evidence of decompensated liver disease manifested by the presence of or history of ascites, esophageal or gastric variceal bleeding, hepatic encephalopathy, or other signs or symptoms of active advanced liver disease.
4. is classified as Child-Pugh B or C or has a Child Pugh-Turcotte score (CPT) > 6 :

NOTE: To calculate the Child-Pugh score, refer to the following website:
<http://www.mdcalc.com/child-pugh-score-for-cirrhosis-mortality>

5. has cirrhosis and liver imaging within 6 months of Day 1 showing evidence of hepatocellular carcinoma (HCC) or is under evaluation for HCC.

NOTE: If liver imaging within 6 months of Day 1 not available, imaging is required during screening.

6. is hepatitis B surface antigen [HBsAg] positive at screening.

NOTE: Subjects who are HBsAg negative at screening, but who are hepatitis B core antibody (anti-HBc) positive at screening may be included. For all anti-HBc positive subjects, hepatitis B virus (HBV) deoxyribonucleic acid (DNA) will be assessed at screening, and both HBV DNA and HBsAg will be monitored during the trial. Additional details can be found in Section 7.1.3.4 – HBV Evaluation and Section 7.2.3.2 – Events of Clinical Interest.

7. is under evaluation for active or suspected malignancy, except for adequately treated basal cell or squamous cell skin cancer or *in situ* cervical cancer.
8. is taking or plans to take any of the prohibited medications listed in **Section 5.5**.
9. is currently participating or has participated in a study with an investigational compound within 30 days of signing informed consent and is not willing to refrain from participating in another such study during the course of this study.
10. has clinically-relevant drug or alcohol abuse within 12 months of screening, in the opinion of the investigator that would compromise the patient's ability to participate in the trial.
11. is a female and is pregnant or breastfeeding, or expecting to conceive or donate eggs from Day 1 through 14 days after the last dose of study drug or longer if dictated by local regulations, OR a male subject who is expecting to donate sperm from Day 1 through 14 days after the last dose of study drug or longer if dictated by local regulations.
12. has any clinically-significant illness (other than HCV) or any other major medical disorder that in the opinion of the investigator may interfere with subject treatment, assessment or compliance with the protocol or any medical/surgical conditions that may result in a need for hospitalization during the period of the study; subjects currently under evaluation for a potentially clinically-significant illness (other than HCV) are also excluded.

NOTE: Subjects with a history of acute non-HCV-related hepatitis, which resolved > 6 months before study entry, can be enrolled.

13. has exclusionary laboratory values at the screening visit as listed in [Table 10](#)

NOTE: If any of the laboratory exclusion criteria in [Table 10](#) are met, the site may have the abnormal value retested once. No other tests may be repeated for determining study entry eligibility.

Table 10 Laboratory Exclusion Criteria

Laboratory Assessment	Exclusionary Parameters
Hemoglobin	< 10 g/dL in females or < 11 g/dL in males
Platelets	< $40 \times 10^3/\mu\text{L}$
Serum Albumin	< 3.0 g/dL
INR	> 1.7 (unless subject has known hemophilia or is stable on an anticoagulant regimen affecting INR)
ALT	> $10 \times \text{ULN}$
AST	> $10 \times \text{ULN}$

14. Is or has an immediate family member (e.g., spouse, parent/legal guardian, sibling or child) who is investigational site or sponsor staff directly involved with this trial.

